#### **General Information**

#### 1.0 Purpose

1.1 The purpose of this clinical study is to validate the SpO2 accuracy of the Stryker Sustainability Solutions pulse oximetry sensors during motion conditions over the range of 70-100% SaO2 as compared to arterial blood samples assessed by CO-Oximetry during conditions in which the subject is moving. The end goal is to provide supporting documentation for the SpO2 accuracy validation of the reprocessed sensors with motion indications.

In this study, the level of oxygen within the blood will be reduced in a controlled manner by reducing the concentration of oxygen the study volunteer breathes. The accuracy of a noninvasive pulse oximeter sensor will be assessed by comparison to the oxygen saturation measurements from a laboratory blood gas analyzer.

A machine will be used to induce motions of 20 mm during testing at a sine rate of 2Hz, 3Hz, and 4Hz. A third motion moves the arm a random distance of 0 to 30mm at a random speed up to 5Hz.

It is required that the Accuracy Root Mean Square (ARMS) performance of the Stryker pulse oximetry sensors will meet a specification of +/-3% with a target of +/-3% or better in motion conditions for the range of 70 - 100% SaO2 (typically, saturation is determined once with air breathing and then at three or six levels, e.g. 94%, 90%, 85%, 80%, 75% and 70% or 95%, 85% and 75% saturation for about 30-60 seconds or 60-90 seconds at each level), thereby demonstrating an acceptable SpO2 accuracy performance specification. This study should utilize a three level structure (95%, 85% and 75%).

**1.2** This study is being conducted to support a modification to the regulatory body approval of pulse oximeter probes reprocessed by Stryker Sustainability Solutions.

#### 2.0 Scope

2.1	This procedure applies to the following Stryker Sustainability Solutions location(s):

	⊠ Tempe	□ Phoenix	□ Lakeland		☐ Chandler
--	---------	-----------	------------	--	------------

2.2 This study has been designed to include the subject devices listed in Table 1.

Study Device:			
OM	SKU	Minimum Quantity	Cycle Count
Masimo	4000 Adt (Adult)	10	4x
Masimo	4003 Neo (Adult & Neonate)	10	4x

Table 1: Subject devices

#### 4.0 Related Documents

4.1 DWI-CDS-109, Division Engineering Study Templates

DF-CDS-109-11	UNCONTROLLED WHEN PRINTED
Rev. L	STRYKER CONFIDENTIAL - This document contains confidential and proprietary
Sustainability Document Template	information that is the property of Stryker Corporation. Neither this document nor the information herein may be reproduced, used or disclosed to any third party without the prior written consent of Stryker Corporation.

Document No:	CRD10351
Revision:	Α
Page:	2 of 11

- 4.2 DWI-CDS-112, Division Engineering Study Exceptions
- **4.3** DWI109.650, New Product Development Training Form
- 4.4 CRD10352, Post Launch Hypoxia Clinical Study Report for Reprocessed Masimo RD SET Pulse Oximeters with Motion
- 4.5 TR22597, Post Launch Sample Preparation Report for Reprocessed Masimo RD SET Pulse Oximeters
- **4.6** CQD-CCA-001 Conducting Clinical Research
- **4.7** CQP-CCA-002 Approval of Clinical Research Proposals, Protocols, Study Design Documents and Publications
- 4.8 DSOP587 Division Conducting Clinical Research
- 4.9 D0000065949 Investigator Initiated Studies
- 4.10 DP-MCF-001, Division Complaint Handling Process
- 4.11 DP-CDS-013, Risk Management

#### 5.0 Key Terms

Refer to CQM-02, Stryker Corporation Quality and Regulatory Master Glossary, for definitions to the Key Terms used within this document.

- **5.1 Allocation:** A method used to assign participants to an arm of a clinical study. The types of allocation are randomized allocation and nonrandomized.
- **5.2 Arm:** A group or subgroup of participants in a clinical trial that receives a specific intervention/treatment, or no intervention, according to the trial's protocol.
- **5.3 Eligibility criteria:** The factors that allow someone to participate in a clinical study are called inclusion criteria, and the factors that disqualify someone from participating are called exclusion criteria. They are based on characteristics such as age, gender, the type and stage of a disease, previous treatment history, and other medical conditions.
- **5.4 Intervention/treatment:** A process or action that is the focus of a clinical study. Interventions include drugs, medical devices, procedures, vaccines, and other products that are either investigational or already available. Interventions can also include noninvasive approaches, such as education or modifying diet and exercise.
- **5.5 Masking:** A clinical trial design strategy in which one or more parties involved in the trial, such as the investigator or participants, do not know which participants have been assigned which interventions. Types of masking include: open label, single blind masking, and double-blind masking.
- **5.6 Primary outcome measure:** In a clinical study's protocol, the planned outcome measure that is the most important for evaluating the effect of an intervention/treatment. Most clinical studies have one primary outcome measure, but some have more than one.
- **5.7 Study type:** Describes the nature of a clinical study. Study types include interventional studies (also called clinical trials), observational studies (including patient registries), and expanded access.

#### **Procedure**

#### 7.0 **Summary**

Study Design:	T	
Study Type:	Interventional Non-significant Risk Lab Test	
Enrollment:	A typical study wi	ll include at least 10 subjects (up to 24 if needed to reach the 200
	necessary data po	oints to meet the ISO 80601-2-61:2019).
Allocation:	Non-randomized	
Intervention Model:	Parallel Assignmen	nt
Intervention Model Description:	Subjects will reclin	ne for the study. Reference sensors will be placed on each subject
	to evaluate the Sp	OO 2 accuracy and performance. Shield material may be used
	between any adjacent finger sensors to prevent optical crosstalk. A machine will	
	be used to induce motions of up to 20 mm during testing at a sine rate of 2Hz, 3Hz,	
	and 4Hz. A third motion moves the arm a random distance of up to 30mm at a	
	random speed up to 5Hz. Simultaneous data collection will be set up for devices	
	under test. The data from the test devices will be collected by the sponsor or	
	trained UCSF staff. Data will be collected for 1 second intervals data analysis. The	
	SpO 2 accuracy of the test devices will be evaluated over the oxygen saturation	
	range between 70-100%.	
Masking:	None (Open Label)	
Primary Purpose:	Device Validation	
Study Start Date:	May 27-28, 2023	
Arms and Interventions:		
Experimental: Masimo RD SET SpO2	2 Adhesive	Device: Stryker Sustainability Solutions Reprocessed Masimo
Sensors, Adult (4000 Adt), Adult & Neonate (4003		RD SET Pulse Oximetry Sensors

Neo)

Reference sensors from the reprocessed oximeter device will be placed on each subject to evaluate the SpO2 accuracy and performance.

An oximeter is a device used to transmit radiation at a known wavelength(s) through blood and to measure the blood oxygen saturation based on the amount of reflected or scattered radiation. Pulse oximetry monitoring is considered a standard physiological measurement and is used by clinicians in everyday situations to estimate arterial oxygen saturation. Because an arterial sample of blood is not required to make the measurement, the pulse oximeter can provide non-invasive real time information.

DF-CDS-109-11	UNCONTROLLED WHEN PRINTED
Rev. L	STRYKER CONFIDENTIAL - This document contains confidential and proprietary
Sustainability Document Template	information that is the property of Stryker Corporation. Neither this document nor the information herein may be reproduced, used or disclosed to any third party without the prior written consent of Stryker Corporation.

Document No:	CRD10351
Revision:	Α
Page:	4 of 11

Sham Comparator: Radiometer ABL-90 multiwavelength oximeter

A whole blood analyzer (CO-Oximeter) is used as the reference standard device for obtaining the functional SaO2 value from arterial blood samples obtained during the study.

Device: CO-OXIMETRY SENSORS

A whole blood analyzer (CO-Oximeter) is used as the reference standard device for obtaining the functional SaO2 value from arterial blood samples obtained during the study.

#### **Primary Outcome Measures:**

 Accuracy of Sensor by Arms Calculation [ Time Frame: 1-5 hours ]

Percentage of SpO2 (oxygen saturation by pulse oximetry) measured by the Reprocessed Oximeter pulse oximetry sensors during motion conditions over the range of 70-100% SaO2 as compared to arterial blood samples assessed by CO-Oximetry.

The Accuracy root mean square (ARMS) between measured  $SpO_2$  and reference  $SaO_2$  (arterial oxygen saturation) must meet the 3% specification for each Stryker Sustainability Reprocessed pulse oximetry sensor style.

Accuracy will be determined by comparing the noninvasive blood oxygen saturation measurement of the pulse oximeter to that obtained from a blood sample and calculating the arithmetic root mean square error (Arms) value. In order to obtain the Arms value, the blood oxygen saturation measurement is subtracted from the pulse oximeter oxygen saturation measurement for a number of samples, the average of this difference is computed as the bias. The standard deviation of the differences is computed as the precision. The square root of the sum of the squares of bias and precision is computed as the Arms Error value.

For each range specified, SpO2 ACCURACY of the PULSE OXIMETER EQUIPMENT shall be stated in terms of the root-mean-square (rms) difference between measured values ( $SpO_{2i}$ ) and reference values ( $S_{Ri}$ ), as given by the following formula.

$$A_{\mathrm{rms}} = \sqrt{\frac{\displaystyle\sum_{i=1}^{n} \left(Sp\mathrm{O}_{2i} - S_{\mathrm{R}i}\right)^{2}}{n}}$$

#### **Eligibility Criteria:**

Ages Eligible for Study: ≥18 and <50 (Adult)

Sexes Eligible for Study: All Accepts Healthy Volunteers: Yes

Inclusion and	Exclusion	Criteria
---------------	------------------	----------

#### Inclusions:

- The subject is male or female, aged ≥18 and <50

- The subject is in good general health with no evidence of any medical problems.
- The subject is fluent in both written and spoken English
- The subject has provided informed consent and is willing to comply with the study procedures

DF	-C	DS	3-1	109	-11	
Re	٧.	L				
_					_	

Sustainability Document Template

#### UNCONTROLLED WHEN PRINTED

**STRYKER CONFIDENTIAL** – This document contains confidential and proprietary information that is the property of Stryker Corporation. Neither this document nor the information herein may be reproduced, used or disclosed to any third party without the prior written consent of Stryker Corporation.

Document No:	CRD10351
Revision:	A
Page:	5 of 11

	

Exclusions:

The subject is obese (BMI>30)

	1
	The subject has a known history of heart disease, lung disease, kidney or liver disease
	Diagnosis of asthma, sleep apnea, or use of CPAP
	Subject has diabetes
	Subject has a clotting disorder
	The subject a hemoglobinopathy or history of anemia, per subject report or
	the first blood sample, that in the opinion of the investigator, would make them unsuitable for study participation
	The subject has any other serious systemic illness
	The subject has any other serious systemic limess     The subject is a current smoker
	
 
Any injury, deformity, or abnormality at the sensor sites that in the opinion of
 

	the investigators would interfere with the sensors working correctly
	The subject has a history of fainting or vasovagal response
	The subject has a history of sensitivity to local anesthesia
	The subject has a diagnosis of Raynaud's disease
	The subject has unacceptable collateral circulation based on exam by the
	investigator (Allen's test)
	The subject is pregnant, lactating or trying to get pregnant
	The subject is unable or unwilling to provide informed consent, or is unable or
	unwilling to comply with study procedures
	The subject has any other condition, which in the opinion of the investigators
	would make them unsuitable for the study
Contacts and Locations:	
Locations	United States, California
	University of California, San Francisco
Sponsors and Collaborators	Stryker Sustainability Solutions, [name] (study monitor)
Investigators	Principal Investigator:
	[name], MD, PhD, CA License # is [name] Co-
	Principal Investigator:
	[name], MD

#### 8.0 Product Description

- **8.1 Intended Use:** Reprocessed Masimo RD SET Pulse Oximeter Sensors are indicated for single patient use for continuous noninvasive arterial oxygen saturation and pulse rate monitoring.
- **8.2 Principle of Operation:** The principle of operation of pulse oximetry is based upon the fundamental principle that hemoglobin bound to oxygen (oxyhemoglobin) and hemoglobin unbound to oxygen (deoxyhemoglobin) vary in the absorption of different wavelengths of the light and the absorptions can be used to estimate SpO2 and PR. The mechanism by which this process occurs is the use of red and infrared wavelengths of light delivered by an emitter and the detection of the signal from the light absorption of oxygenated blood and deoxygenated blood to determine functional oxygen saturation of hemoglobin (SpO2).
- **8.3 Mechanism of Action for Achieving the Intended Effect:** The Reprocessed Pulse Oximeter Sensor provides the intended effect equivalent to the previously cleared pulse oximeter sensor in that it utilizes an optical sensor that is applied to the patient's finger or toe through which light is transmitted to the photodetector that detects the signal transmission. The signal transmission is processed by the Pulse Oximeter to provide SpO2 and PR.

DF-CDS-109-11	UNCONTROLLED WHEN PRINTED
Rev. L	STRYKER CONFIDENTIAL – This document contains confidential and proprietary
Sustainability Document Template	information that is the property of Stryker Corporation. Neither this document nor the information herein may be reproduced, used or disclosed to any third party without the prior written consent of Stryker Corporation.

Document No:	CRD10351
Revision:	Α
Page:	6 of 11

# Reprocessed Masimo RD SET Pulse Oximeter Sensor

4000 Adt

# Reprocessed Masimo RD SET Pulse Oximeter Sensor

#### 9.0 Worst Case Justification

9.1 The pulse oximeter sensors which are identified in Table 1 as subject devices have received FDA clearance for a maximum of four (4) reprocessing cycles. Sensors used in this study were subjected to the maximum number of reprocessing cycles. Catalog number 4000 consists of a non-woven butterfly style tape and catalog number 4003 consists of a woven style tape. There is no worse case model in that the characteristics of both tape types are equivalent within the model family and do not present different challenges during the tape removal process when reprocessing.

#### 10.0 Sample Size Designation

- 10.1 A typical study will include at least 10 subjects (up to 24 if needed to reach the 200 necessary data points to meet the ISO 80601-2-61:2019). Per FDA guidance, at least 2 or 15% of the subjects will have dark skin pigmentation. Skin pigmentation will be assessed using the Fitzpatrick scale by UCSF study personnel.
- 10.2 Each study subject will have two reprocessed sensors attached to their fingers. Two Reprocessed Masimo RD SET sensors should be placed on one side of the subject; however, sensors may be placed opposite sides. Digits selected should be two of the three middle fingers on each hand avoiding the thumb or pinky fingers as test sites.

#### 11.0 Preliminary Investigations and Justification of the Study

- **11.1** Stryker Sustainability Solutions has developed a process to reprocess pulse oximeters that cleans and disinfects the devices active element components and device cord and replaces all patient contacting tapes. The foam covering the cable is cleaned and disinfected but not replaced during reprocessing.
- **11.2** The manufacturing process for reprocessing includes 100% visual inspection and functional assessment.
- **11.3** As part of the product development and validation phases of this project, Stryker has performed the following studies:
  - Cleaning
  - Disinfection
  - Biocompatibility
  - Performance

#### 12.0 Study Devices

DF-CDS-109-11	UNCONTROLLED WHEN PRINTED
Rev. L	STRYKER CONFIDENTIAL - This document contains confidential and proprietary
Sustainability Document Template	information that is the property of Stryker Corporation. Neither this document nor the information herein may be reproduced, used or disclosed to any third party without the prior written consent of Stryker Corporation.

Document No:	CRD10351
Revision:	Α
Page:	7 of 11

#### 12.1 Device Accountability

- **12.1.1** Devices will be transported to the test site by the study sponsor.
- 12.1.2 Use of Study Device
  - **12.1.2.1** Use of devices will be documented electronically as case reports for each subject.

#### 12.2 Packaging and Labeling

12.2.1 Research conducted for this study will utilize investigational devices. The Sponsor is responsible for packaging and labeling of the devices for delivery to the study site. Investigational devices or its immediate package shall bear a label with the following information:

"CAUTION – Investigational device. Limited by Federal (or United States) law to investigational use".

#### 13.0 Procedure

- 13.1 If the principal investigator deems it necessary, the subject may be asked to run hot water over hands and arms for 5 minutes to improve perfusion. After injection of a local anesthetic, a 22-gauge catheter is inserted in one radial artery. Pulse oximeters are attached to fingers with adequate spacing between fingers or shielding to minimize device cross-talk. Subjects are in a comfortable semi-recumbent position. Subjects then breathe air mixtures containing reduced amounts of oxygen to produce the desired level of hypoxemia. Stable, safe and controlled hypoxia is adjusted manually by an anesthesiologist that permits the inspired gas mixture to be adjusted to achieve a level of lung alveolar gas that will achieve the desired degree of saturation.
- 13.2 Typically, saturation levels involve one period with air breathing and then at one of three or six levels, e.g. 94%, 90%, 85%, 80%, 75% and 70% or 95%, 85% and 75% saturation. Each level of saturation is held for 30-60 seconds or 60-90 seconds respectively. At appropriate intervals and when oxygen levels are stable, arterial blood samples are obtained from the radial arterial catheter. The operator then changes the inspired oxygen concentration to attain the next desired stead-state level of hypoxia. This study should utilize a three level structure (95%, 85% and 75%). A "run" consists of several stable steady-state hypoxia levels and together takes approximately 20 minutes. Each run is terminated by a breath of 100% O2 followed by room air. Two runs together enable obtaining a total of 20-25 blood samples, 4 samples at each plateau. Saturation of each arterial blood sample is determined by direct oximetry in a Radiometer ABL-90 multi-wavelength oximeter. The precise target levels of saturation can be adjusted to suit the sponsor, but typical testing is done to satisfy ISO and FDA standards for testing, which is 70% to 100%.
- **13.3** The study takes under 2 hours of each subject's time. Analysis of the data requires several days. Manufacturer's representatives (Stryker) will be present for these tests, and to mount the probes.

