#### 25.0 Acceptance Criteria

- 25.1 The statistical results of the data will be reviewed for the following pass/fail criteria:
  - **25.1.1** At least 200 data points with SpO2 Accuracy for the range of 70-100%, 3% (ARMS) is considered a Pass per FDA guidance.
  - **25.1.2** At least 10 participants where at least two participants or 15% of participant population will have dark skin pigmentation per the Fitzpatrick scale.

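### Accuracy is to be declared down to 70% SaO2, but the lowest target is 75% and no rule ties the declared lower limit to the SaO2 reached

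*Combined protocol and SAP*

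**What the plan says.** Three places set the range. Section 1.1 aims to validate accuracy "during motion conditions over the range of 70-100% SaO2". The primary outcome concerns the "sensors during motion conditions over the range of 70-100" per cent SaO2, with the 3% limit applied to each sensor style. Section 25.1.1 passes the device on at least 200 points with "Accuracy for the range of 70-100%, 3" per cent Arms.

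Section 13.2 describes two possible sets of targets, "94%, 90%, 85%, 80%, 75% and 70% or 95%, 85% and 75% saturation", and then picks the shorter one: "This study should utilize a three level structure (95%, 85% and 75". Section 1.1 makes the same choice. On sampling, 13.2 says "Two runs together enable obtaining a total of 20-25 blood samples, 4 samples at each plateau". On hold times it says "Each level of saturation is held for 30-60 seconds or 60-90 seconds respectively", so the three-level plateaus have the longer hold.

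Some text softens this. Section 13.2 adds that "The precise target levels of saturation can be adjusted to suit the sponsor" and describes typical testing as 70% to 100%. Section 16.2.4 reports error statistics by sub-range without giving cut-points. Section 19.1 points to an ISO clause and annex as a recommendation. None of these, as written in the protocol, requires any pairs near 70% or links the declared lower limit to the SaO2 reached.

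**The concern.** The lower limit of a declared accuracy range should be a value the data reach. Here the only route to the lowest two or three points is a plateau that misses its target on the low side. The protocol's own six-level option has a 70% plateau; the three-level choice drops it while the declared range stays the same.

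The pass rule pools all pairs, so it would not reveal thin support at the edge. A table row for 70-80% would not either, because most of its pairs would lie around 75%. At stake is what a pass means: section 1.2 says the study is to support a regulatory modification, and a pass could be stated down to 70% with the bottom of the range resting largely on extrapolation from readings around 75%.

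**Working it through.** **Draws per subject.** Reading 13.2 as four draws per plateau in each of two runs, 2 × 3 × 4 = 24, plus one on air = 25, which matches the stated 20-25. Ten subjects at 20-25 draws give 200-250 pairs, which reproduces the minimum of 200 in 15.1.

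**Share at the lowest plateau.** 2 × 4 = 8 of 25 draws, so 8/25 × 200 = 64 of 200 pairs. For the six-level option, four draws per plateau over both runs give 6 × 4 + 1 = 25, so 4/25 × 200 = 32 pairs per plateau. Counts below are for 200 pairs of one sensor style.

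**Assumption.** The documents give neither the scatter of achieved SaO2 nor its mean at a plateau. I take normal scatter with mean m and SD s of 1, 1.5, 2 or 2.5 points. The expected count between a and b is n × [Φ((b − m)/s) − Φ((a − m)/s)], summed over plateaus.

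Worked for 70-73% at s = 2:
- As planned, m = 75: 64 × [Φ(−1) − Φ(−2.5)] = 64 × (0.1587 − 0.0062) = 9.8.
- Plateaus averaging 74: 64 × [Φ(−0.5) − Φ(−2)] = 64 × (0.3085 − 0.0228) = 18.3.
- 73% in one run, 75% in the other: 32 × [Φ(0) − Φ(−1.5)] + 32 × 0.1524 = 13.9 + 4.9 = 18.7.

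| Expected pairs of 200 | SD 1 | SD 1.5 | SD 2 | SD 2.5 |
|---|---|---|---|---|
| 70-75%, target 75% | 32 | 32 | 32 | 31 |
| 70-73%, target 75%, mean 75 | 1.5 | 5.8 | 9.8 | 12.1 |
| 70-73%, target 75%, mean 74 | 10 | 16 | 18 | 19 |
| 70-73%, split 73%/75% | 17 | 18 | 19 | 18 |
| 70-73%, six-level option | 17 | 18 | 19 | 18 |
| 75-80%, target 75% | 32 | 32 | 32 | 32 |
| 75-80%, split 73%/75% | 17 | 19 | 21 | 23 |
| Below 70%, target 75% | 0 | 0 | 0.4 | 1.5 |
| Below 70%, split 73%/75% | 0 | 0.7 | 2.3 | 4.4 |
| Below 70%, six-level option | 16 | 16 | 16 | 17 |

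As a yardstick, an even spread over the 30 points would put 5/30 × 200 = 33 pairs in 70-75% and 3/30 × 200 = 20 in 70-73%. The wider band meets its share; the narrower one falls short when plateaus centre on 75%.

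**Chance of no pair at all in 70-73%.** Ten subjects with eight low draws each give 80 draws. Treating them as independent, the chance is (1 − p)^80. At s = 1, p = 0.0227 and the chance is 16%. At s = 1.5, p = 0.0908 and it is about 0.05%. Correlation within subjects would raise these figures.

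**What the pooled rule can see.** Suppose Arms is 2.5 outside 70-73% and 3.5 inside. With w pairs inside, pooled Arms = √{[(200 − w) × 2.5² + w × 3.5²]/200}. This runs from 2.51 to 2.57 for w = 1.5 to 12.1, and is about 2.60 to 2.61 for w = 17 to 19: a pass either way. In the other direction, with 10 of 200 pairs (5%) in the band and Arms 2.0 elsewhere, Arms in the band could reach √[(9 − 0.95 × 4)/0.05] = 10.2 before the pooled value reached 3.0. That describes the rule's sensitivity; it does not predict sensor error.

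**The case against.** **The thinness is assumed.** The documents give no plateau scatter, and gas is adjusted by hand. An average undershoot of one point yields about 10, 16, 18 and 19 pairs in 70-73%, close to the proposed split from an SD of 1.5 up. This stands, and it is why the size of the gap is left open. But a protocol should not depend on missing its own target to cover its declared range.

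**The even-spread yardstick is not in the plan, and other gaps are larger.** Under the same model 78.5-81.5% holds about 0, 1.3, 5.1 and 9.7 pairs, fewer than 70-73%. This is correct. The difference is that an interior gap has data on both sides, whereas the bottom edge has data on one side only.

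**The pass decision would not change.** This stands too. In the Arms example above, the split moves the pooled value by less than 0.1, and nothing in the documents suggests that accuracy changes sharply between 75% and 70%.

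**Other text may cover it.** Targets may be adjusted, sub-ranges are reported, and the ISO clause named in 19.1 may hold a coverage rule. The first permits a change without requiring one, and the second has no consequence in 25.1. The ISO text is not in the documents, so the claim is only that no such rule is written out here. It does not establish departure from the standard.

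**Stronger readings.** A reader might infer that 70-75% is unsampled, or that a pass would be false. Neither follows: about 32 of 200 pairs are expected in that band, some pairs in 70-73% are likely unless scatter is very small, and no effect on the pooled result has been shown.

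**Conclusion.** The mismatch is in the text: the range is declared to 70%, the lowest target is 75%, and no written rule connects the declared limit to the SaO2 obtained. The consequence is confined to the lowest two or three points. With plateaus centred on 75%, 70-73% would hold about 0.7% to 6% of pairs (1.5 to 12.1 of 200), clearly thin at an SD of 1 to 1.5 and modestly so at 2 to 2.5. With plateaus averaging 74%, most of the shortfall disappears from an SD of 1.5 up. These figures rest on normal scatter, on the assumed means and SDs, and on the reading of 13.2 that gives 64 low draws per 200. The point should be addressed because the remedy is small and the declared limit is the study's main claim. Confidence in its size is medium.

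**What to change.** 1. **Sections 1.1 and 13.2:** set the lowest target at 73% in one run and 75% in the other. Section 13.2 already allows targets to be adjusted, and no subjects or draws are added. Using 73% in both runs is a poorer trade, since it thins 75-80% to about 1.5, 6, 11 and 15 pairs.
2. **Section 25.1.1:** state that, for each sensor style, the declared lower limit may not be below the lowest SaO2 its pairs support. Write in the deciding number before data are seen, or cite the clause of the standard that sets it. A minimum count in 70-73% is a workable form: with the split that row is expected to hold 17 to 19 pairs at any of the SDs tried. If the count is not met, the declared limit becomes 73%.
3. **Section 16.2.4:** give pair counts and Arms per sensor style for 70-80, 80-90 and 90-100%, with 70-73% as a separate row.

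**Costs.** Hypoxia is slightly deeper in one run, at the 60-90 second hold. About 0, 0.7, 2.3 and 4.4 of 200 draws would fall below 70%, against 0, 0, 0.4 and 1.5 as planned and about 16 in the six-level option; section 18.1 says values below 70% are not sought. If plateaus also run one point low (72% and 74%), the count is 32 × [Φ(−2/s) + Φ(−4/s)], or about 0.7, 3.0, 5.8 and 8.5. The 75-80% band drops from 32 to about 17-23 pairs. IRB approval is already in place (22.4), so the amendment needs review under 22.3. If the sponsor keeps 75%, items 2 and 3 still apply, and the declared range may end a few points narrower than 70-100%.
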